### **12.2.8. Worst-Case Abnormality**

Derived per parameter separately, for abnormalities only.

Three worst-case determinations will be done, depending on the chapter of analysis:

1. Including all nonmissing post-baseline values, including “use=No” and unscheduled measurements, up to and including the Week 12 value. Also including the follow-up value in case the subject did not participate in the second period of the study. If the subject participated in the second period of the study, then the follow-up value will be included in the worst-case of the second period of the study, not of the first period.
2. Including all nonmissing post-Week 12 values, including “use=No” and unscheduled measurements, up to and including the follow-up value.
3. Including all nonmissing post-baseline values, including “use=No” and unscheduled measurements, up to and including the follow-up value.

#### **12.2.8.1. According to normal ranges**

Possible categories:

- H = abnormally high: at least one postdose measurement is above the normal range, and there are no values below the normal range.
- L = abnormally low: at least one postdose measurement is below the normal range, and there are no values above the normal range.
- H+L = abnormally high and low: at least one postdose measurement is above the normal range, and at least one other postdose measurement is below the normal range.
- N = normal: all postdose measurements are within normal limits.

#### **12.2.8.2. According to CTCAE tox grades**

The worst-case is the highest post-baseline tox grade.

#### **12.2.8.3. According to the ATP III classifications**

The worst-case is the highest post-baseline class for LDL, total cholesterol and triglycerides.  
The worst-case is the lowest post-baseline class for HDL.

## 12.2.9. Tables up to Week 12

No formal inferential statistics (p-values) will be derived. Time points to present: screening, baseline, Weeks 1-2-4-8-12, last on-treatment, worst case.

If the subject did not participate in the second period of the study, then the follow-up visit will be presented in the table of the first period of the study. If the subject participated in the second period of the study, then the follow-up value will be presented in the table of the second period of the study, not of the first period.

### **Table 14.3.2.1: Laboratory data up to Week 12: Descriptive statistics of the actual values per time point**

Descriptive statistics of actual values per lab test category (hematology, biochemistry, endocrine, urinalysis), lab test and unit, treatment group and time point.

Population: safety.

Population: safety, selecting subjects with a baseline value within normal range (for endocrine tests only).

Table to be created for the Week 12 interim analysis as well.

### **Table 14.3.2.2: Laboratory data up to Week 12: Descriptive statistics of the changes from baseline per time point**

Descriptive statistics of changes from baseline per lab test category (hematology, biochemistry, endocrine, urinalysis), lab test and unit, treatment group and time point. The actual value at baseline will also be presented in this table.

Population: safety.

Population: safety, selecting subjects with a baseline value within normal range (for endocrine tests only).

Table to be created for the Week 12 interim analysis as well.

### **Table 14.3.2.3: Laboratory data up to Week 12: Descriptive statistics of the percent changes from baseline per time point**

Descriptive statistics of percent changes from baseline per lab test category (hematology, biochemistry, endocrine, urinalysis), lab test and unit, treatment group and time point. The actual value at baseline will also be presented in this table.

Population: safety.

Population: safety, selecting subjects with a baseline value within normal range (for endocrine tests only).

Table to be created for the Week 12 interim analysis as well.

**Table 14.3.2.4: Laboratory data up to Week 12: Shift table of the lab abnormalities per time point**

Shift table per lab test category (hematology, biochemistry, endocrine, urinalysis), lab test, treatment group and time point. The table will present the shift in abnormality (L/N/...) at worst-case and last on-treatment (other time points: not needed) versus the baseline abnormality (L/N/H). Tests without normal ranges will not be presented in this table.

Population: safety.

**Table 14.3.2.5: Laboratory data up to Week 12: Treatment-emergent lab abnormalities per time point**

Frequency table of the treatment-emergent lab abnormalities per lab test category (hematology, biochemistry, endocrine, urinalysis), lab test, treatment group and time point (including the worst-case). A post-baseline abnormality is considered treatment-emergent if it differs from the baseline result. Tests without normal ranges will not be presented in this table.

Population: safety.

Table to be created for the Week 12 interim analysis as well.

**Table 14.3.2.6: Laboratory data up to Week 12: Frequency table of the CTCAE toxicity grades per time point**

Frequency table (with cumulative percentages) per lab test category (hematology, biochemistry, endocrine, urinalysis), lab test, treatment group and time point.

Table for selected tests only.

Population: safety.

Table to be created for the Week 12 interim analysis as well.

**Table 14.3.2.7: Laboratory data up to Week 12: Shift table of the CTCAE toxicity grades per time point**

Shift table per lab test category (hematology, biochemistry, endocrine, urinalysis), lab test, treatment group and time point. The table will present the shift in CTCAE tox grade (0/1/2/3/4) at worst-case and last on-treatment (other time points: not needed) versus the baseline grade (0/1/2/3/4).

Table for selected tests only.

Population: safety.

**Table 14.3.2.8: Laboratory data up to Week 12: Treatment-emergent CTCAE toxicity grades per time point**

Frequency table of the treatment-emergent lab CTCAE tox grades per lab test category (hematology, biochemistry), lab test, treatment group and time point (including worst-case). A

post-baseline grade is considered treatment-emergent if it is higher than the baseline tox grade.

Table for selected tests only.

Population: safety.

Table to be created for the Week 12 interim analysis as well.

**Table 14.3.2.9: Laboratory data up to Week 12: Frequency table of the ATP III classes per time point**

Frequency table (with cumulative percentages) per lab test category (hematology, biochemistry, endocrine, urinalysis), lab test, treatment group and time point.

Table for selected tests only.

Population: safety.

Table to be created for the Week 12 interim analysis as well.

**Table 14.3.2.10: Laboratory data up to Week 12: Shift table of the ATP III classes per time point**

Shift table per lab test category (hematology, biochemistry, endocrine, urinalysis), lab test, treatment group and time point. The table will present the shift in ATP III class at worst-case and last on-treatment (other time points: not needed) versus the baseline class.

Table for selected tests only.

Population: safety.

**Table 14.3.2.11: Laboratory data up to Week 12: Treatment-emergent ATP III classes per time point**

Frequency table of the treatment-emergent lab ATP III classes per lab test category (hematology, biochemistry), lab test, treatment group and time point (including worst-case). A post-baseline class is considered treatment-emergent if it differs from the baseline result and is of higher category.

Table for selected tests only.

Population: safety.

Table to be created for the Week 12 interim analysis as well.

**Table 14.3.2.12: Laboratory data up to Week 12: Frequency table of percent changes from baseline per time point in inhibin B and testosterone**

Frequency table of the percent changes from baseline per lab test category (endocrine), lab test, treatment group and time point. The percent changes from baseline will be categorized

as: <-50%, [-50%,+50%], >+50%. A worst-case will also be shown selected as the lowest post-baseline value.

Table only for inhibin B, free testosterone, total testosterone.

Population: safety – males.

Population: safety, selecting male subjects with a baseline value within normal range.

Table to be created for the Week 12 interim analysis as well.

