### 12.2.5.2. CTCAE V3.0 gradings for biochemistry tests

CTCAE version 3.0 classification is only for the below tests. For other tests, only the classification according to normal ranges will be done.

Lab test	Grade 0	Grade 1	Grade 2	Grade 3	Grade 4
Albumin (g/L)	≥ LLN	[30,LLN[	[20,30[	<20	(NAP)
ALT, AST, alkaline phosphatase and γGT	≤ ULN	]1.0,2.5] x ULN	]2.5,5.0] x ULN	]5.0,20.0] x ULN	> 20.0 x ULN
Amylase and lipase	≤ ULN	]1.0,1.5] x ULN	]1.5,2.0] x ULN	]2.0,5.0] x ULN	> 5.0 x ULN
Total bilirubin	≤ ULN	]1.0,1.5] x ULN	]1.5,3.0] x ULN	]3.0,10.0] x ULN	> 10.0 x ULN
Calcium low (mmol/L)	≥ LLN	[2.00,LLN[	[1.75,2.00[	[1.50,1.75[	<1.50
Calcium high (mmol/L)	≤ ULN	]ULN,2.9]	]2.9,3.1]	]3.1,3.4]	>3.4
Total cholesterol (mmol/L)	≤ ULN	]ULN,7.75]	]7.75,10.34]	]10.34,12.92]	>12.92
Creatinine	≤ ULN	]1.0,1.5] x ULN	]1.5,3.0] x ULN	]3.0,6.0] x ULN	> 6.0 x ULN
Glucose low (mmol/L)	≥ LLN	[3.0,LLN[	[2.2,3.0[	[1.7,2.2[	<1.7
Glucose high (mmol/L)	≤ ULN	]ULN,8.9]	]8.9,13.9]	]13.9,27.8]	>27.8
Phosphate (mmol/L)	≥ LLN	[0.8,LLN[	[0.6,0.8[	[0.3,0.6[	<0.3
Potassium low (mmol/L)	≥ LLN	[3.0,LLN[	(NAP)	[2.5,3.0[	<2.5
Potassium high (mmol/L)	≤ ULN	]ULN,5.5]	]5.5,6.0]	]6.0,7.0]	>7.0
Sodium low (mmol/L)	≥ LLN	[130,LLN[	(NAP)	[120,130[	<120
Sodium high (mmol/L)	≤ ULN	]ULN,150]	]150,155]	]155,160]	>160
Triglycerides	≤ ULN	]1.0,2.5] x ULN	]2.5,5.0] x ULN	]5.0,10.0] x ULN	> 10.0 x ULN

Note:

– LLN = lower normal limit

- ULN = upper normal limit
- (NAP) = grade does not exist.

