### **12.2.11. Tables over the whole 24 weeks period**

The same tables will be made as for the first period of the study, but with the 11 adapted treatment groups. Time points to present: screening, baseline, Week 1-2-4-8-12, last on-treatment during period 1, worst case during period 1, Weeks 16-20-24, last on-treatment during period 2, follow-up (all follow-up visits in the study), worst case during period 2, last on-treatment during the whole study, worst case during the whole study. Population: Safety.

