**Table 14.3.2.23: Laboratory data over the whole study: Shift table of the ATP III classes per time point**

**Table 14.3.2.24: Laboratory data over the whole study: Treatment-emergent ATP III classes per time point**

**Table 14.3.2.25: Laboratory data over the whole study: Frequency table of percent changes from baseline per time point in inhibin B and testosterone**

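### The treatment-emergent rule for ATP III classes runs the wrong way for HDL: it flags rises and can never flag a fall to below 40 mg/dL

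*SAP*

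**What the plan says.** SAP section 12.2.5.4 classifies four lipids by ATP III and lists every set of classes in ascending order of concentration. For HDL there are three: below 40, 40 to below 60, and 60 mg/dL or above.

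Section 12.2.8.3 sets the adverse direction by lipid. The highest class is worst for LDL, total cholesterol and triglycerides, but for HDL: "The worst-case is the lowest post-baseline class for HDL".

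Table 14.3.2.11 (section 12.2.9) then gives one rule for all ATP III tests, at each time point and in the worst-case row: a "post-baseline class is considered treatment-emergent if it differs from the baseline result and is of higher category".

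Section 12.2.11 carries this to 24 weeks: "The same tables will be made as for the first period of the study", with adapted treatment groups. The counterpart is Table 14.3.2.24, "Treatment-emergent ATP III classes per time point". It has three worst-case rows: period 1, period 2 and the whole study.

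**The concern.** A row labelled treatment-emergent in a laboratory safety table is read as a count of deteriorations. For HDL, the rule counts movements in the direction that the SAP itself treats as favourable. The wording parallels the CTCAE rule of Table 14.3.2.8, where a "post-baseline grade is considered treatment-emergent if it is higher than the baseline tox grade". That works for CTCAE because a higher grade is always worse. It does not carry over to a classification in which one of the four tests runs the other way.

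Lipid changes matter for this drug class. Protocol section 6.1 reports raised HDL with an approved JAK inhibitor. If GLPG0634 behaves similarly, the HDL rows would fill with rises presented as treatment-emergent findings, while any falls would be absent from them. The protocol gives no reason to expect falls, so the concern is a misleading table and not a predicted harm.

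**Working it through.** The plan gives no figure to reproduce; the check is to apply the rule to every possible case.

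**Inputs.** HDL classes from SAP 12.2.5.4, coded 1 (below 40), 2 (40 to below 60) and 3 (60 or above). Worst case = minimum class (12.2.8.3). Rule as written: flagged if the post-baseline class is above the baseline class (Table 14.3.2.11). Consistent rule: flagged if it is below the baseline class.

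**Single time point.**

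| Change | As written | Consistent with 12.2.8.3 |
|---|---|---|
| 1 to 2 | flagged | no |
| 1 to 3 | flagged | no |
| 2 to 3 | flagged | no |
| 2 to 1 | no | flagged |
| 3 to 1 | no | flagged |
| 3 to 2 | no | flagged |

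All three rises are flagged and no fall is. Class 1 has nothing beneath it, so a post-baseline value below 40 can never satisfy the rule.

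**Worst-case row to Week 12.** With the five scheduled visits (Weeks 1, 2, 4, 8, 12) there are 3 × 3^5 = 3 × 243 = 729 combinations of baseline and post-baseline classes.

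- As written (minimum above baseline): baseline 1 needs every visit in class 2 or 3, giving 2^5 = 32; baseline 2 needs every visit in class 3, giving 1; baseline 3 gives 0. Total 33, and in each of them every visit is above baseline.
- Consistent rule (minimum below baseline): baseline 1 gives 0; baseline 2 gives 243 − 32 = 211; baseline 3 gives 243 − 1 = 242. Total 453.
- No pattern is flagged by both rules.
- Patterns with baseline 40 or above and at least one value below 40: 2 × (243 − 32) = 422. The rule as written flags none of them.

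These are counts of patterns, not probabilities or expected patients.

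**Other lipids.** For LDL, total cholesterol and triglycerides the worst case is the maximum class, so the rule and the worst-case direction agree in every pattern.

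**What other tables supply.**

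- Table 14.3.2.9 is a "Frequency table (with cumulative percentages) per lab test category": it gives classes at each visit, but not change from baseline.
- Table 14.3.2.10 shows the "shift in ATP III class at worst-case and last on-treatment" against baseline, and no other time points.
- The CTCAE tables do not help: "CTCAE version 3.0 classification is only for the below tests", and HDL is not listed.
- Table 14.3.2.5 would show HDL only against the laboratory's normal range, if one is supplied, and not against the ATP III cut-offs.
- The descriptive tables and mean plots show average HDL, not individual class changes.

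The number of subjects at each visit who are newly in a lower HDL class than at baseline is therefore tabulated only in the rows with the reversed rule. Table 14.3.2.11 is also marked for the Week 12 interim analysis and shift Table 14.3.2.10 is not, so the interim output has no ATP III display of HDL falls relative to baseline.

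**The case against.** Several points can be made on the other side.

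- **Higher category might mean higher risk.** The SAP assigns no risk ranks, and section 12.2.8.3 uses highest and lowest literally, reversing the direction for HDL in words. The literal reading is the one a programmer would follow.
- **HDL might not be in the table.** The table is restricted to selected tests that are not named, and the mock tables are in a separate document. This is a fair caveat. But HDL is one of only four ATP III tests, and its worst case is defined specifically for this classification, so inclusion is the natural reading.
- **The information survives elsewhere.** This largely stands. Besides the tables above, section 12.2.2 derives the TC/HDL and LDL/HDL ratios with upper limits. These are analysed with the other tests, so a falling HDL could show in Table 14.3.2.5 through a raised ratio. The laboratory listings also carry the ATP III class. However, the ratios depend on the other lipid too and need not cross their limits, and listings are not tabulated counts.
- **The pattern counts show no patient impact.** Correct; they only describe the rule. The SAP's worst case also admits unscheduled values and, for subjects who do not enter period 2, the follow-up value. That changes the number of patterns but not the direction of the error.
- **The tables are descriptive.** Also correct: no p-value, endpoint or sample size depends on them.

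**Conclusion.** The concern holds. By the SAP's own definition of the HDL worst case, the HDL rows of Tables 14.3.2.11 and 14.3.2.24 report the favourable direction and omit the unfavourable one: three of three rises flagged, none of three falls. The conclusion assumes that HDL is among the selected tests and that category order follows the ascending listing in section 12.2.5.4; both are the natural readings of the text.

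The consequence is limited. HDL falls are not lost from the report, and the documents give no expected number of HDL class changes from which to estimate how many subjects are affected. The correction should be made because the error is clear, concerns safety reporting and is cheap to remove. It does not bear on the primary analysis.

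**What to change.** Replace the rule with: a post-baseline ATP III class is treatment-emergent if it is worse than the baseline class, meaning higher for LDL, total cholesterol and triglycerides, and lower for HDL. This matches section 12.2.8.3. Apply it to the final Tables 14.3.2.11 and 14.3.2.24, and check that the mock tables agree.

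Record the change in SAP section 6.3. Version 5.0 postdates the interim database lock, so only the final tables can change; footnote that HDL rows in any interim version produced under the present wording used the opposite direction. The pharmacodynamic addendum says it was written after unblinding, so if the final tables already exist the entry belongs in section 6.3.3 as a post-lock correction. Because it follows a direction already stated in the SAP, it is not a results-driven choice.

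The cost is one sentence, a small programming change, a log entry and a footnote, using data already collected.

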**Table 14.3.2.13: Laboratory data up to Week 12: Shift table of the categorical lab data per time point**

Shift table per lab test category (hematology, biochemistry, endocrine, urinalysis), lab test, treatment group and time point. Selecting only the tests with categorical data. The table will present the shift in value at each post-baseline time point versus the baseline value.

Population: safety.

**12.2.10. Figures up to Week 12**

**Figure 14.3.2.1: Laboratory data up to Week 12: Mean plots of the actual values over time**

Mean plots of the actual values over time, with each lab test on a new page but with all treatment groups on the same plot using different plot symbols. Unscheduled or follow-up results will not be part of this plot.

Population: safety.

Figure to be created for the Week 12 interim analysis as well.

**Figure 14.3.2.2: Laboratory data up to Week 12: Mean plots of the changes from baseline over time**

Mean plots of the changes from baseline over time, with each lab test on a new page but with all treatment groups on the same plot using different plot symbols. Unscheduled or follow-up results will not be part of this plot. With a horizontal reference line at zero, indicating no change. Plots will start with a zero mean at baseline.

Population: safety.

Figure to be created for the Week 12 interim analysis as well.

**Figure 14.3.2.3: Laboratory data up to Week 12: Mean plots of the percent changes from baseline over time**

Mean plots of the percent changes from baseline over time, with each lab test on a new page but with all treatment groups on the same plot using different plot symbols. Unscheduled or follow-up results will not be part of this plot. With a horizontal reference line at zero, indicating no change. Plots will start with a zero mean at baseline.

Population: safety.

Figure to be created for the Week 12 interim analysis as well.

### **12.2.11. Tables over the whole 24 weeks period**

The same tables will be made as for the first period of the study, but with the 11 adapted treatment groups. Time points to present: screening, baseline, Week 1-2-4-8-12, last on-treatment during period 1, worst case during period 1, Weeks 16-20-24, last on-treatment during period 2, follow-up (all follow-up visits in the study), worst case during period 2, last on-treatment during the whole study, worst case during the whole study. Population: Safety.

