**Table 14.3.2.26: Laboratory data over the whole study: Shift table of the categorical lab data per time point**

### 12.2.12. Figures over the whole 24 weeks period

The follow-up visit will not be shown on the mean plots because it is expected that it will happen only for a limited number of subjects, as a large number will roll over into study 205 without a follow-up visit.

The same plots again, but with the 11 adapted treatment groups. Plots will show data from screening up to the end of the study.

**Figure 14.3.2.4: Laboratory data over the whole study: Subject profile plots over time – subjects with a treatment-emergent abnormality**

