## **12.4.7. Tables over the whole 24 weeks period**

The same tables again, but with adapted treatment groups focusing on the subjects who used GLPG0634 during both study periods. Time points to present: screening, baseline, Week 1-2-4-8-12, last on-treatment during period 1, worst case during period 1, Weeks 16-20-24, last on-treatment during period 2, last on-treatment during the whole study, follow-up (all follow-up visits in the study), worst case during period 2, worst case during the whole study.

Population: Safety.

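### In the 24-week laboratory and vital-sign tables, the period 1 worst case rests on 5 scheduled samples and the period 2 worst case on 3 or 4, so comparing the two rows is biased toward fewer abnormalities in period 2

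*SAP*

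**What the plan says.** Protocol 8.7.1.4.2 has the safety laboratory tests done at every visit, and the flow chart shows the same for vital signs. After baseline that means Weeks 1, 2, 4, 8 and 12 in period 1 and Weeks 16, 20 and 24 in period 2.

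For the 24-week laboratory tables, SAP 12.2.11 gives the rows, after screening and baseline, as "Week 1-2-4-8-12, last on-treatment during period 1, worst case during period 1, Weeks 16-20-24, last on-treatment during period 2". From Week 16 on, the list runs "Weeks 16-20-24, last on-treatment during period 2, follow-up (all follow-up visits in the study), worst case during period 2". SAP 12.4.7 lists the same elements for vital signs, including "worst case during period 1, Weeks 16-20-24, last on-treatment during period 2".

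SAP 12.2.8 and 12.4.5 define the worst case over all nonmissing values in the period, unscheduled and non-selected ones included. The period 2 version covers "unscheduled measurements, up to and including the follow-up value". For a subject who entered period 2, "then the follow-up value will be included in the worst-case of the second period of the study, not of the first period". Only early discontinuers and subjects not entering study 205 have a Follow-up visit, and SAP 12.2.12 expects that "a large number will roll over into study 205 without a follow-up visit".

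The laboratory shift tables for normal ranges, CTCAE grades and ATP III classes present the shift "at worst-case and last on-treatment (other time points: not needed"). The vital-sign shift table is limited in the same way. SAP 12.2.7 and 12.4.4 define last on-treatment as a single value per subject and period, without Follow-up.

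The laboratory tables use the 11 safety groups of SAP 2.1.2. Two of these took placebo in period 1 and GLPG0634 in period 2.

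**The concern.** The chance that a subject has at least one abnormal value in a period cannot fall, and normally rises, as more samples are taken. Five samples against three is therefore not a like-for-like comparison, yet the two rows appear in the same table, for the same columns, under parallel labels. No denominator rule or footnote warns the reader.

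In columns on a constant dose, abnormalities may seem to settle with longer exposure when nothing has changed. In the two laboratory columns switched from placebo, the row pair reads as before and after starting GLPG0634, and the unequal counts pull against seeing an increase on drug. Coverage also varies within a column, because some period 2 worst cases include a post-treatment Follow-up value and others do not. These are the tables from which laboratory safety by treatment sequence will be read.

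**Working it through.** **Inputs from the documents.** Scheduled samples behind the worst case: k = 5 in period 1 (Weeks 1, 2, 4, 8, 12). In period 2, k = 3 (Weeks 16, 20, 24) for a subject who rolls over to study 205, and k = 4 for one with a Follow-up visit.

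**Assumptions.** The documents give neither an abnormality rate nor a within-subject correlation, and no figure of their own to reproduce here. The per-sample rate p is varied from 1% to 20% and held equal in both periods. Correlation is varied from none to complete.

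**Step 1: independent samples.** P(at least one abnormal) = 1 − (1 − p)^k. At p = 5%: 1 − 0.95^5 = 22.6%; 1 − 0.95^3 = 14.3%; 1 − 0.95^4 = 18.5%.

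| p | Period 1 (k = 5) | Period 2 (k = 3) | Period 2 with Follow-up (k = 4) |
|---|---|---|---|
| 1% | 4.9% | 3.0% | 3.9% |
| 2% | 9.6% | 5.9% | 7.8% |
| 5% | 22.6% | 14.3% | 18.5% |
| 10% | 41.0% | 27.1% | 34.4% |
| 20% | 67.2% | 48.8% | 59.0% |

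The ratio of period 2 to period 1 is 0.61 to 0.73 with three samples and 0.80 to 0.88 with four.

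**Step 2: mixed Follow-up coverage.** If a share f of subjects has a Follow-up visit, the period 2 rate at p = 5% is f × 18.5% + (1 − f) × 14.3%. For f = 10%, 25% and 50% this gives 14.7%, 15.3% and 16.4%, against 22.6% in period 1.

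**Step 3: correlated samples.** Two models at p = 5%, k = 5 against k = 3. The latent-normal model has a subject effect on an underlying normal scale; the beta-binomial model places the correlation on the yes/no outcome itself, so equal values of the coefficient do not mean equal dependence.

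| Correlation | Latent normal | Beta-binomial |
|---|---|---|
| 0.5 | 16.6% v 11.8% | 11.0% v 8.9% |
| 0.8 | 11.7% v 9.3% | 7.1% v 6.5% |
| 1 | 5.0% v 5.0% | 5.0% v 5.0% |

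The direction is the same in both models; the size depends on the model. With complete persistence there is no gap.

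**Step 4: what can be hidden in the placebo-switch laboratory columns.** Find the period 2 rate q at which the worst cases are equal: 1 − (1 − q)^3 = 1 − (1 − p)^5, so q = 1 − (1 − p)^(5/3). At p = 5%, q = 8.2%, a 1.64-fold rise that would show as no change. With latent-normal correlation 0.5, q = 7.3%. With independent samples, a 1.5-fold rise (7.5%) shows as a fall, from 22.6% to 1 − 0.925^3 = 20.9%. A doubling (10%) shows as a rise, to 1 − 0.9^3 = 27.1%.

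**Step 5: equal counts.** With three scheduled samples in each period, p = 5% and independence, both rates are 14.3%. Weeks 4, 8, 12 and Weeks 16, 20, 24 also share the same 4-week spacing, so a correlation that decays with time does not reopen the gap.

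**The case against.** The strongest reply is that the reader already has comparisons free of the sample count. Last on-treatment is one value per subject and period, excludes Follow-up, and appears in the 24-week tables and in the shift tables. Per-visit rows appear in the treatment-emergent, CTCAE and ATP III frequency tables. This stands, and it confines the problem to the worst-case rows. A reader might infer that the shift tables leave no comparable view between periods; the definition of last on-treatment shows otherwise.

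A reader might also infer that worst-case rates must fall from period 1 to period 2. They need not: the gap closes for persistent abnormalities, and a doubling at 5% still shows as a rise. It is a downward bias whose size is unknown in advance.

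Nor do the tables distort the placebo comparison in general. Columns compared within a period share one visit schedule, and the randomised comparison is the 12-week analysis of the seven original groups. The placebo-to-drug reading arises only within two laboratory columns, made up of placebo non-responders. For vital signs, SAP 12.4.7 describes groups focusing on subjects on GLPG0634 in both periods, so that reading is not clearly supported there.

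Finally, safety is descriptive and no p-values are planned. That limits the consequence, but the misleading row pair remains. The all-sample period worst cases should not be replaced: they hold early and unscheduled values and, for placebo switchers, the only all-sample worst case on GLPG0634.

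**Conclusion.** The point holds for one pair of rows. In the 24-week laboratory and vital-sign tables, the all-sample worst cases of the two periods rest on 5 and on 3 or 4 scheduled samples, and comparing them favours period 2. At a constant assumed 5% per sample, the size ranges from 22.6% v 14.3% (independent, no Follow-up) through 16.6% v 11.8% or 11.0% v 8.9% (correlation 0.5, by model) to no gap under full persistence. In the two laboratory switch columns, a rise of up to about 1.6-fold could go unseen at 5% with independent samples. The sample counts come from the plan; the rates and correlations are assumptions. Unscheduled values enter both periods and are not modelled. No efficacy result or formal test is touched, so this is an inexpensive improvement in presentation.

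**What to change.** In SAP 12.2.8 and 12.4.5, add a supplementary period-matched worst case: scheduled Weeks 4, 8 and 12 for period 1, and scheduled Weeks 16, 20 and 24 for period 2, without unscheduled or Follow-up values. Show it in the 24-week tables, including shift tables 14.3.2.17, 14.3.2.20, 14.3.2.23 and 14.3.4.9. Keep the existing all-sample worst cases for period 1, period 2 and the whole study beside it. Add a footnote that the all-sample period rows rest on different numbers of samples and should not be compared between periods.

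The cost is SAP wording, one more derived record per subject, test and period, and one more table row per test and period. The matched row leaves out Week 1, Week 2, unscheduled and Follow-up values, which stay in the all-sample rows. It equalises the planned counts; missed visits and dropout in period 2 can still leave fewer actual samples there.
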